Appendix 3: List of Ocular Drying or Increased Lacrimation Medications

The following classes of concomitant medications are prohibited if the specific concomitant medication is known to cause ocular drying or increased lacrimation (i.e. ocular dryness or increased lacrimation is listed among the AEs or side effects section of the medication's labeling) and the medication has not been used at a stable dose for at least 30 days prior to Visit 1.

Ocular Drying

- Antihistamines
- Anti-depressants
- β -blockers
- Antipsychotic
- Codeine
- Decongestants
- Diuretics

Increased Lacrimation

- Cholinergic drugs

Appendix 5: Amendment Summary of Changes

Not applicable

Appendix 8: COVID-19 PANDEMIC AND SUGGESTED MEASURES

This section is provided in response to the “FDA Guidance on Conduct of Clinical Trials of Medical Products during COVID-19 Pandemic Public Health Emergency” issued by the FDA on March 2020 and updated on August 2021. Taking the COVID-19 impact into account, this section provides guidance to Investigators and their site staff to mitigate risks and suggested measures to modify operations. Each Investigator may choose to implement different measures according to their sites’ operations; which may include, but are not limited to the following items.

Screening Questions to Identify Potential COVID-19 Exposure

When scheduling an on-site visit for subjects, consider asking the subjects a few, short questions regarding potential exposure to COVID-19 before their on-site visit (in-person interactions). For example:

1. Have you had any of the following symptoms in the past 14 days without confirmation of etiology such as a positive flu test, existing chronic medical condition, etc.
 - Fever greater than 100.4 dgres
 - Fahrenheit
 - Cough
 - Difficulty breathing
 - Sore throat
2. In the last 14 days, have you lived with, visited, cared for, or been in a room for a prolonged period of time with someone who is under investigation or has been confirmed for COVID-19?

Remote Monitoring

Due to travel restrictions, shelter in place or stay at home mandates, sites’ change in operations, and a number of other reasons to try to contain the spread of the virus and minimize exposure, it is reasonable to conduct monitoring visits remotely, instead of in-person, whenever feasible. Site staff/Investigator will work with CRO and the assigned CRA to define and understand the logistics of the remote visit such as source data verification.

Data Management

In order to confirm the effect of COVID-19 on this study, the following information will be captured in eCRF.

- Missed visit due to COVID-19
- Missed assessment due to COVID-19

- Screen failed subject due to COVID-19
- Early discontinuation due to COVID-19
- AE related to COVID-19

tCFS	Total Corneal Fluorescein Staining
TE-SAE	Treatment-Emergent Serious Adverse Event
TEAE	Treatment-Emergent Adverse Event
TFBUT	Tear Film Break-Up Time
TMF	Trial Master File
WHODrug	World Health Organization Drug Dictionary

1 Introduction

The purpose of this statistical analysis plan (SAP) is to describe the planned analyses and reporting in detail for the efficacy and safety assessments of study 614/1132 as well as relevant data collected in protocol 614/1132, Version 1.0 dated 23MAR2022.

This SAP is being written with due consideration of the recommendations outlined in the most recent International Conference on Harmonisation (ICH) E9 Guideline entitled Guidance for Industry: Statistical Principles for Clinical Trials, the most recent ICH E9 (R1) Guideline entitled Guidance for Industry: Statistical Principles for Clinical Trials: Addendum: Estimands and Sensitivity Analysis in Clinical Trials, and the most recent ICH E3 Guideline, entitled Guidance for Industry: Structure and Content of Clinical Study Reports.

The statistical analysis methods presented in this document will supersede the statistical analysis methods described in the clinical protocol. If additional analyses are required to supplement the planned analyses described in this SAP, they may be completed and will be identified in the clinical study report.

2 Study Objectives

The objective of this study is to evaluate the efficacy and safety of 0.3% SI-614 ophthalmic solution compared with placebo when administered 4 times daily (QID) for 84 days in patients with dry eye.

3 Study Design and Procedures

3.1 General Study Design

This study is a Phase 3, multicenter, randomized, double-masked study to evaluate the efficacy and safety of 0.3% SI-614 Ophthalmic Solution compared to placebo in patients with dry eye. Approximately 230 patients will be randomized with a ratio of 1:1 into one of the two groups: (1) 0.3% SI-614, or (2) placebo, which they will be instructed to administer QID for 84 days. The randomization will be stratified by two factors:

- Average of dryness and ocular discomfort at bedtime assessment based on run-in patient daily diary mean from Day-7 through Day -1: ≤ 2.5 vs > 2.5
- Change [REDACTED] in total corneal fluorescein staining at Visit 2: ≤ 3.5 vs. > 3.5

Table 1 shows the scheduled study visits, their planned study day (note that there is no Day 0 and that Day 1 corresponds to the day of randomization), and the acceptable visit window for each study visit:

Table 1. Study Visit Windows

Scheduled Visit	Planned Study Day	Visit Window
Visit 1	Day -14	± 3 Days
Visit 2	Day 1	N/A
Visit 3	Day 8	± 2 Days
Visit 4	Day 15	± 2 Days
Telephone Visit 1	Day 22	± 2 Days
Visit 5	Day 29	± 3 Days
Telephone Visit 2	Day 43	± 2 Days
Visit 6	Day 57	± 3 Days
Telephone Visit 3	Day 71	± 2 Days
Visit 7	Day 85	± 3 Days

3.2 Schedule of Visits and Assessments

The schedule of visits and assessments is provided in [Appendix 1](#).

4 Study Variables

4.1 Primary Efficacy Endpoint

The primary efficacy endpoint is the following:

- Change from baseline (CFB) [REDACTED] to Day 29 [REDACTED] in total corneal fluorescein staining (tCFS) score on the [REDACTED] Scale in the study eye.
 - Fluorescein staining will be conducted at all visits, including all [REDACTED] time points.
 - Grading of the [REDACTED] region will be conducted using the [REDACTED] Corneal and Conjunctival Staining Scale, which is a 0 to 4 scale [REDACTED] and where grade 0 = No Staining and 4 = Confluent Staining.
 - The tCFS score is derived using the sum of the [REDACTED] regions such that possible scores range from 0 to 12.

4.1.1 STATISTICAL HYPOTHESES OF PRIMARY ENDPOINT

The statistical hypotheses are stated in terms of one-sided hypotheses, at a significance level of 0.025.

H_{01} : The change from baseline Visit 2 (Day 1, [REDACTED] to Visit 5 (Day 29, [REDACTED] in tCFS score [REDACTED] of the study eye for 0.3% SI-614 is equal or greater than placebo.

H_{A1} : The CFB Visit 2 (Day 1, [REDACTED] to Visit 5 (Day 29, [REDACTED] in tCFS score [REDACTED] [REDACTED] of the study eye for 0.3% SI-614 is less than placebo.

4.1.2 ESTIMANDS

- **Estimand 1**: If the rate of intercurrent events such as lack of efficacy or adverse events (AEs) for the primary endpoint is balanced between the two treatment groups (as evaluated by the Fisher's exact test at an alpha level of 0.05) and the rate of intercurrent events for the endpoint is $\leq 5\%$ in all patients, the intercurrent events for the primary analysis will be handled using Estimand 1. The proposed strategies listed in Estimand 1 for the primary analyses will potentially provide a relatively conservative treatment effect based on the assumptions associated with each intercurrent event.

The rate of intercurrent events for primary efficacy endpoint will be summarized by treatment group and overall, with Fisher's exact test p-value.

The following intercurrent events will be considered in Estimand 1:

- Non-optimal compliance is ignored. Measures will be analyzed regardless of treatment compliance [treatment policy strategy], assuming the non-compliance is not associated with the assigned treatments.
- Use of prohibited concomitant medications is ignored. Measures obtained after use of prohibited concomitant medications will be analyzed [treatment policy strategy], assuming more patients from the placebo group would experience this intercurrent event.
- Treatment discontinuation due to lack of efficacy before the assessment of the primary endpoint. Missing values assumed to be missing not at random (MNAR) will be multiply imputed using placebo group-based pattern mixture model (PMM) imputation [hypothetical strategy], assuming more patients in the placebo group would experience this intercurrent event.
- Treatment discontinuation due to AEs before the assessment of the primary endpoint. Missing values assumed to be missing not at random (MNAR) will be imputed using placebo group-based pattern mixture model (PMM) imputation [hypothetical strategy], assuming more patients in the treatment group would experience this intercurrent event.
- Treatment discontinuation due to reasons other than lack of efficacy or AEs, assumed to be missing at random (MAR), will be multiply imputed using randomized treatment group-based Markov Chain Monte Carlo (MCMC) imputation. [hypothetical strategy]

- Five subjects were randomized using incorrect stratification data at Visit 2, resulting in mis-randomization if correct strata were used. Those subjects will be analyzed as randomized with the correct baseline information.
- **Estimand 2:** If the rate of intercurrent events such as lack of efficacy or AEs for the endpoint is imbalanced between treatment groups (demonstrated by Fisher's exact test with a p-value of <0.05) and the rate of intercurrent events for the endpoint is greater than 5% in all patients, then the primary analyses will utilize ITT population with Estimand 2. The trimmed mean approach will be applied to the primary analyses. The patients' data, missing or non-missing, will be trimmed if the patients experience the intercurrent events such as treatment discontinuation due to lack of efficacy or treatment discontinuation due to AEs. The permutation test will be used to test the treatment difference. The trimmed proportion is as shown on Table 2.

Table 2. Proportions of Data Trimmed

Maximum Rate of intercurrent events in any treatment group (%)	Data Trimmed (%)
5% to <10%	10%
10% to <20%	20%
20% to <30%	30%

The following intercurrent events will be considered in Estimand 2:

- Treatment discontinuation due to lack of efficacy or AEs before the assessment of the primary endpoint – will be trimmed irrespective of missingness or not
- Missing data as results of treatment discontinuation due to reasons other than lack of efficacy or AEs, assumed to be MAR, will be multiply imputed using randomized treatment group-based MCMC imputation. [hypothetical strategy]
- Non-optimal compliance is ignored. Measures will be analyzed regardless of treatment compliance [treatment policy strategy], assuming the non-compliance is not associated with the assigned treatments.
- Use of prohibited concomitant medications is ignored. Measures obtained after use of prohibited concomitant medications will be analyzed [treatment policy strategy]
- Subjects who were mis-randomized will be analyzed as randomized using the correct baseline information.

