in the study eye at Day 28. The majority of AEs were mild in severity and no AEs were severe. No serious adverse events (SAEs) were reported. The most frequently reported ocular TEAE and non-ocular TEAE were instillation site pain (20 [16.4%] patients in the 0.3% SI-614 group and 16 [13.6%] patients in the placebo group) and nosopharyngitis (4 [3.3%] patients in the 0.3% SI-614 group and 3 [2.5%] patients in the placebo group). Four TEAEs led to the premature discontinuation of 2 patients; 1 patient in the 0.3% SI-614 group (conjunctivitis right eye, conjunctivitis left eye) and 1 patient in the placebo group (conjunctivitis right eye, conjunctivitis left eye). No safety concerns were raised in terms of visual acuity and slit lamp biomicroscopy assessments.

Potential Risks: Based on the results of Phase 2 and Phase 2/3 studies with SI-614, the most likely AEs that patients may experience include instillation site reactions, and, possibly but less likely, reduced visual acuity. AEs reported in published safety data from clinical trials of HA ophthalmic solutions in dry eye patients included worsening of dry eye symptoms, eye pain, or foreign body sensation. Additionally, based on results from animal studies with SI-614, patients may also experience discharge and redness of the eye.

Potential Benefits: Patients may experience a reduction in various signs and symptoms of dry eye.

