11.4.4 Primary Efficacy Analyses

For the primary endpoint, change from baseline will be calculated as visit – baseline such that a positive difference indicates a worsening of dry eye signs. In addition, treatment comparisons between 0.3% SI-614 and placebo will be calculated as 0.3% SI-614 – placebo, such that a negative result indicates a better score for 0.3% SI-614 (i.e., 0.3% SI-614 demonstrated less severity in dry eye signs than the placebo group).

The primary analysis of the primary endpoint will use the ITT population. If the rate of missing data for an endpoint is balanced between the two treatment groups (as evaluated by the Fisher's exact test at an alpha level of 0.05) or the rate of missing data for the endpoint is $\leq 5\%$ in all subjects then primary analysis will be executed using ANCOVA with multiple imputation methodology using the following Estimand 1:

Estimand 1:

- Population:
 - ITT population
- Endpoint:
 - Change from baseline [REDACTED] in total corneal fluorescein staining score in the study eye at Day 29 [REDACTED] in the ITT population
- Intercurrent event:

- Discontinuation of study medications is ignored. Measures obtained after discontinuation of study medication will be analyzed. [treatment policy strategy]
- Non-optimal compliance is ignored. Measures will be analyzed regardless of treatment compliance. [treatment policy strategy]
- Use of prohibited concomitant medications is ignored. Measures obtained after use of prohibited concomitant medications will be analyzed. [treatment policy strategy]
- Withdrawal due to lack of efficacy or adverse events. Missing values assumed to be missing not at random will be multiply imputed using placebo group-based PMM imputation. [hypothetical strategy]
- Missing data with withdrawal or withdrawal due to reasons other than lack of efficacy or adverse events. Missing values assumed to be missing at random will be multiply imputed using randomized treatment group-based MCMC imputation. [hypothetical strategy]

- Population-level summary:
 - Difference in the mean change from baseline [REDACTED] in total corneal fluorescein staining score in the study eye at Day 29 [REDACTED] between 0.3% SI-614 and placebo in the ITT population.

The permutation test with trimmed means as specified in Estimand 2 will then be executed as additional sensitivity analyses.

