7.1 Input Data

Study data will primarily be recorded on the eCRFs supplied by [REDACTED] using [REDACTED]

When all prerequisites for database lock have been met, the database will be locked. Following database lock, approval will be obtained from the Sponsor to unmask the study. Any changes to the database after data have been locked can only be made with the approval of the Sponsor in consultation with [REDACTED].

Final analysis will be carried out after the following have occurred:

- Database lock has occurred with written authorization provided by appropriate [REDACTED] and Sponsor personnel.
- Protocol deviations have been identified and status defined (major/minor deviations) prior to database lock.
- Analysis populations have been determined.
- Randomized treatment codes have been unmasked.

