14.1 Primary Efficacy Endpoint

14.1.1 PRIMARY ANALYSIS METHODS

Primary analysis of the CFB [REDACTED] to Day 29 [REDACTED] in tCFS will be performed using an Analysis of Covariance(ANCOVA) model adjusted for baseline value with treatment group as the explanatory variable on ITT population with Estimand 1 or ITT population with Estimand 2 depending on the rate of intercurrent events. Least squares (LS) means for each treatment group and the LS mean difference comparing 0.3% SI-614 with placebo will be presented from the model together with SEs, two-sided 95% CIs, and one-sided p-values.

Subject listings will be provided for the primary efficacy endpoint for all randomized patients.

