15.4 Pregnancy Test

A urine pregnancy test will be conducted for female patients of childbearing potential at Visit 1 (Day -14) [REDACTED] Visit 7 (Day 85) [REDACTED] and may be conducted at unscheduled visits during the study. A patient listing of urine pregnancy test results will be generated.

16 Interim Analyses

No interim analyses are planned.

17 Subgroup Analysis by Two Stratification Factors

Subgroup analysis of the primary efficacy endpoint will be performed in subgroups of each stratification factor using the ITT population with the observed data only. For the five subjects who were mis-randomized, the subgroup assignments will first be based on the strata at randomization and then based on the strata of the correct baseline information. The primary endpoint will be analyzed using an ANCOVA model including baseline values and treatment group as covariates on the ITT population with the observed data only. LS means and their respective SEs will be presented from the ANCOVA model along with their two-sided 95% CIs for each treatment group. LS mean difference comparing 0.3% SI-614 treatment to placebo will be presented from the model with SEs, two-sided 95% CIs, and one-sided p-values.

18 Changes from Protocol-Stated Analyses

The intercurrent events described in the Estimands 1 and 2 in the study protocol is not appropriate for two reasons. The intercurrent events may or may not lead to missing data. The missing data may or may not be due to intercurrent events. Missing data are described in the missing data handling section if the missing is not the results of the intercurrent events.

19 References

MJ; Gorst-Rasmussen A;Tarp-Johansen. "Fast Tipping Point Sensitivity Analyses in Clinical Trials with Missing Continuous Outcomes under Multiple Imputation." *Journal of Biopharmaceutical Statistics*, U.S. National Library of Medicine, <https://pubmed.ncbi.nlm.nih.gov/35653556/>.

20 Revision History

Documentation of revision to the SAP will commence after approval of the final version 1.0.

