On May 27, 2023, it was identified that five subjects were randomized using incorrect stratification data at Visit 2, resulting mis-randomization if the correct strata were used. The SAP was revised before the database lock to specify how the mis-randomized subjects will be handled and the impact of the mis-randomization on the primary endpoint will be assessed. Sensitivity analysis and subgroup analysis of the primary efficacy endpoint were added for assessing the impact of the mis-randomization on the primary efficacy endpoint.

21 Tables

Tables that will be included in the topline delivery are shown in **boldface** font.

If Estimand 1 is used for analysis of the primary efficacy endpoint, then tables with Estimand 2 will not be produced. If Estimand 2 is used for analysis of the primary efficacy endpoint, then tables with Estimand 1 will not be produced. Estimand 1 tables have a letter "a" at the end of the table number, and Estimand 2 tables have a letter "b" at the end of the table number.

Table Number	Title	Population
Table 14.1.1	Patient Disposition	All Screened Patients
Table 14.1.2.1	Demographics	ITT Population
Table 14.1.2.2	Demographics	PP Population
Table 14.1.2.3	Demographics	Safety Population
Table 14.1.3.1	Baseline Disease Characteristics	ITT Population
Table 14.1.3.2	Baseline Disease Characteristics	PP Population
Table 14.1.3.3	Baseline Disease Characteristics	Safety Population
Table 14.1.4.1	Ocular Medical History	ITT Population
Table 14.1.4.2	Non-Ocular Medical History	ITT Population
Table 14.1.5.1	Ocular Concomitant Medications	ITT Population
Table 14.1.5.2	Non-Ocular Concomitant Medications	ITT Population

Table Number	Title	Population
Table 14.1.6	The Rate of Intercurrent Events for Primary Efficacy Endpoint at Day 29 [REDACTED]	ITT Population
Table 14.2.1.1a	Summary of Primary Efficacy Analysis for Change from Baseline [REDACTED] to Day 29 [REDACTED] [REDACTED] in Total Corneal Fluorescein Staining [REDACTED] [REDACTED]	ITT Population with Estimand 1
Table 14.2.1.1b	Summary of Primary Efficacy Analysis for Change from Baseline [REDACTED] to Day 29 [REDACTED] [REDACTED] in Total Corneal Fluorescein Staining [REDACTED] [REDACTED]	ITT Population with Estimand 2
Table 14.2.1.2.1a	Summary of Sensitivity Analysis for Change from Baseline [REDACTED] to Day 29 [REDACTED] in Total Corneal Fluorescein Staining [REDACTED]	PP Population with Estimand 1

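### The SAP's rule for choosing the primary estimand covers only two of the four possible outcomes, because the protocol's "or" became "and" with no default stated

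*SAP*

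**What the plan says.** Protocol 11.4.3 and 11.4.4 choose the primary analysis from the rate of missing data. Estimand 1 (ANCOVA with multiple imputation) applies if the rate is balanced by "exact test at an alpha level of 0.05) or the rate of missing data for the endpoint is" no more than 5%. Estimand 2 (trimmed means with a permutation test) applies if the rate is imbalanced and above 5%.

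SAP 4.1.2 applies the choice to intercurrent events instead. For Estimand 1 it requires balance by Fisher's "exact test at an alpha level of 0.05) and the rate of intercurrent events for the endpoint is" no more than 5%. For Estimand 2 it requires imbalance "with a p-value of <0.05) and the rate of intercurrent events for the endpoint is greater than 5% in all patients".

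Other parts of the SAP that bear on the choice:

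- Section 14.1.1 says the primary analysis is run "on ITT population with Estimand 1 or ITT population with Estimand 2 depending on the rate of intercurrent events" and adds no rule of its own.
- Sections 9.2 and 14.1.1.1 repeat that the rate will be summarized with a Fisher p-value. Neither names a default.
- Section 18 gives the reason for leaving the protocol's wording: "The intercurrent events described in the Estimands 1 and 2 in the study protocol is not appropriate for two reasons". The two reasons concern the difference between intercurrent events and missing data. The change of connective is not mentioned.
- Section 21 states: "If Estimand 1 is used for analysis of the primary efficacy endpoint, then tables with Estimand 2 will not be produced". The reverse also applies.
- Section 1 gives the SAP's methods precedence over the protocol's.

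**The concern.** The protocol's two conditions are exact complements, so one of them always holds. The SAP's two conditions are not. If events are balanced but frequent, or imbalanced but rare, neither estimand is selected.

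The rule decides how the single success-defining endpoint, the Day 29 change in total corneal fluorescein staining, is analysed. As SAP 4.1.2 describes them, the two routes differ in estimand and in test. The Fisher comparison needs counts by arm, and the conditions for final analysis in SAP 7.1 include "Randomized treatment codes have been unmasked". If the gap occurred with the text unchanged, the primary analysis would be settled with treatment codes open. Under the protocol's rule nothing would be left to settle.

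A secondary point is that the trigger offers lack of efficacy and adverse events as examples, not as a closed list. The natural reading is treatment discontinuation for either reason before Day 29, but the trigger does not say so.

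**Working it through.** **Step 1: the logic.** Cross the two conditions and read off each document's rule.

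| Outcome | Protocol 11.4.4 | SAP 4.1.2 |
|---|---|---|
| Balanced, ≤5% | Estimand 1 | Estimand 1 |
| Balanced, >5% | Estimand 1 | none |
| Imbalanced, ≤5% | Estimand 1 | none |
| Imbalanced, >5% | Estimand 2 | Estimand 2 |

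Two of four outcomes are unassigned in the SAP. The protocol's rule applies to missing data and the SAP's to intercurrent events, but the logical comparison is the same.

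**Step 2: can the unassigned outcomes occur?** Inputs: 115 patients per arm, 230 in total (SAP 6); balanced means two-sided Fisher p ≥ 0.05; the 5% threshold is read as the pooled rate. Since 11/230 = 4.8% and 12/230 = 5.2%, more than 5% means 12 or more events.

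| Events by arm | Pooled rate | Fisher p | SAP selects |
|---|---|---|---|
| 5 v 0 | 5/230 = 2.2% | 0.060 | Estimand 1 |
| 6 v 0 | 6/230 = 2.6% | 0.029 | none |
| 8 v 1 | 9/230 = 3.9% | 0.035 | none |
| 6 v 6 | 12/230 = 5.2% | 1.0 | none |
| 9 v 3 | 12/230 = 5.2% | 0.135 | none |
| 10 v 2 | 12/230 = 5.2% | 0.034 | Estimand 2 |

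By pooled total:

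- 5 or fewer events: always Estimand 1.
- 6 to 11 events: Estimand 1 or nothing, depending on the split.
- 12 or more events: Estimand 2 or nothing, depending on the split.

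**Step 3: how likely is it?** With independent binomial counts a and b,

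P(gap) = Σ P(a) P(b), summed over pairs with (p ≥ 0.05 and a + b ≥ 12) or (p < 0.05 and a + b ≤ 11).

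The true event rates are assumptions. The one related figure is in Protocol 1.1, for the 28-day Phase 2/3 study of 240 patients: "Four TEAEs led to the premature discontinuation of 2 patients", that is 2/240 = 0.83%. No lack-of-efficacy rate is given.

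| True rate per arm | Balanced, >5% | Imbalanced, ≤5% | P(gap) |
|---|---|---|---|
| 0.83% v 0.83% | 0.0% | 0.03% | 0.03% |
| 1% v 1% | 0.0% | 0.07% | 0.07% |
| 2% v 2% | 0.2% | 0.7% | 0.9% |
| 3% v 3% | 4.5% | 1.3% | 5.8% |
| 4% v 4% | 20.8% | 1.3% | 22.1% |
| 5% v 5% | 47.0% | 0.9% | 47.9% |
| 2% v 1% | 0.02% | 1.0% | 1.0% |
| 3% v 1% | 0.2% | 5.0% | 5.2% |
| 4% v 1% | 0.6% | 12.9% | 13.5% |

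The 5% row is an upper illustration on the narrow reading, because the plan's 5% dropout allowance is for all causes over the whole study.

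**Step 4: after the correction.** With *or* restored for Estimand 1, each of the four outcomes is assigned exactly once and P(gap) = 0 at every rate.

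**The case against.** The strongest reply is that the gap is unlikely to matter.

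- **Likelihood.** At the prior rate of 0.83%, the chance of 5 or fewer pooled events is 98.7%, and Estimand 1 then applies whatever the split. This stands, with the reservation that the prior figure covers adverse events only.
- **Masked monitoring.** Discontinuation reasons are recorded under masking, so the pooled count is known before lock. With 12 or more events the team would see that Estimand 1's threshold had failed and could amend in time. This partly stands. It does not help with 6 to 11 events, where only the arm split decides.
- **Other outputs.** The tables for placebo-based imputation, treatment-group imputation, LOCF, tipping point and observed data (14.2.1.2.2 to 14.2.1.2.11) are produced under either estimand, so alternative results would not be hidden. This stands, but these are sensitivity analyses and do not determine which result is primary.
- **Implied default.** Several tables and Figure 14.1.1a exist only in Estimand 1 form, which suggests Estimand 1 is the intended fallback. One can also argue that the protocol's rule survives wherever the SAP is silent. Both are inferences: no text states the default, and the protocol's rule is framed on missing data.
- **Test.** SAP 14.1.1 names ANCOVA for both estimands, whereas 4.1.2 names a permutation test for Estimand 2. The difference in test is therefore less settled than 4.1.2 alone suggests. The difference in estimand remains.
- **Counted events.** The Estimand 2 text mentions discontinuation for lack of efficacy or adverse events, which largely supports the narrow reading. The trigger itself still leaves the list open.

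These points reduce the weight of the problem. None supplies the missing rule.

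**Conclusion.** The rule is wrong as written: it selects no primary analysis in two of four outcomes, both of which can occur with 115 patients per arm. This conclusion needs no assumption beyond reading the 5% threshold as the pooled rate.

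The practical size does rest on assumptions. On the narrow reading of the counted events the chance of falling in the gap is probably low: 0.03% at the prior 0.83% and under 1% at 2% per arm. It rises to 6% at 3% and 22% at 4%. If the open wording were taken to include non-compliance, prohibited medication or discontinuation for other reasons, rates could be higher; at an assumed 8% per arm the gap would be hit 93.6% of the time. It should be fixed because the rule governs the only success-defining endpoint and the correction is trivial.

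**What to change.** In SAP 4.1.2, replace the two triggers with one exhaustive rule: *Estimand 1 applies unless the intercurrent-event rate is both imbalanced (Fisher p < 0.05) and above 5% overall, in which case Estimand 2 applies.*

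In the same place, state that the events counted for this rule are treatment discontinuations due to lack of efficacy or adverse events before the Day 29 assessment. Record the connective and the final wording in Section 18.

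The cost is SAP wording only, made before unmasking. Data collection and sample size do not change.
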